It will be the responsibility of the research assistants to provide a 'learned' assessment, of what they believe represents a 'typical' pathway at the Nightingale centre. A multidisciplinary team will then assess the validity of this pathway and voice any concerns/objections/potential additions. Once an accurate representation of the existing care pathway has been generated (as agreed by research staff and clinical leads), this will be pilot tested among a group of 10 patients (5 current SOC and 5 Magtrace), in order to ensure that all relevant points of interaction with healthcare staff, and utilisation of health services, are captured, the pathway will be amended as necessary. Using a stopwatch, research staff would have the ability to consent and then actively monitor (shadow around the hospital) a group of ~20 patients in each treatment group (Magtrace® vs. routine care using Technetium nuclear medicine). It is critical prior to recruitment that key covariates and factors likely to influence not only outcomes, but also health economic factors of care are identified. These factors will require consideration before randomisation to Magtrace or routine care, with randomisation recommended to take place using sealed envelopes in blocks of ten. If imbalances in key covariates occur following randomisation, adjustment of health economic outcomes will be performed to mitigate these imbalances using gold-standard two-stage bootstrapping for costeffectiveness analyses.

[figure not shown]
Once data is collected for 20 patients undergoing Magtrace, and 20 patients undergoing routine care, it will be possible to multiply NHS resource utilisation by representative NHS unit costs (staff salaries per minute, radiography, inpatient, nuclear medicine) and determine the array of health economic outcomes listed above. The result will be a health-economic comparison of Magtrace® over Technetium nuclear medicine (Figure 1). Sensitivity analyses will be performed on this dataset to measure the robustness of the findings to changes in the values of the parameters measured during the TDABC stopwatch exercise. Rather than relying on point-estimates, this will enable the derivation of credible intervals, and determine

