how specific factors such as time in the hospital, number of visits, requirement for isotopes etc. each individually affect the overall cost per completed treatment episode. This way, if there are imbalances across treatment groups (whether systematic, for example Magtrace leading to reduced expectation to visit the department repeatedly), or stochastic, due to sampling, these factors will be accounted for in the costing. Furthermore, because it is not necessary to monitor and time every patient over a one-year period (or more), to model the expected annual health-economic benefits of Magtrace®, results observed in this cohort of 40 patients (representative sample) may then be extrapolated to all expected patients/caseload over the course of a calendar year, with the 40 patients observed closely, serving as an estimation set. This is common in cost-effectiveness modelling, and bootstrapping from this cohort of patients to a larger group representative of the full spectrum of clinical caseload over a calendar year, will enable determination of the expected return-on-investment of switching from Technetium nuclear medicine to Magtrace® at the Trust level (or at various levels of implementation/caseload, from 0 to 100%. A previous example of this approach is provided in the reference list vii.

Figure 1: Study flow for health-economic assessment

The Magtrace® will be inserted by trained and qualified healthcare professionals.

The Magtrace® will be injected into the index breast on the day of surgery. The technetium will be injected as per the current pathway on the day of surgery or the day before, technetium is generally used with or without blue dye. Blue dye is injected by the surgeon at the time of surgery and can be used as ab additional tracer with Technetium. It is up to the clinicians' discretion if they use the blue dye at the time of surgery.

Part I Expected duration of patient participation – Four to eight weeks. This will equate to a 2-4 week period between invitation to join study and when surgery occurs. And a 2-3 week period between surgery and the final follow-up study visit.

Identification of potentially eligible patient – done by medical and research team in the breast MDT

Invitation – occurs immediately after surgical discussion on the patient's surgical plan for removal of the breast cancer. Patient given an information leaflet about study (by medical team/breast care nurse/breast research nurse).

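### The interval for the Part 1 cost comparison is to come from sensitivity analyses on stopwatch parameters, which do not by themselves give its sampling error; resampling whole patients within arm would

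*Protocol*

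**What the plan says.** Part 1 times about 20 patients per arm and multiplies their resource use by NHS unit costs. Section 4.2 (Study design, Part 1) sets the comparison out as follows.

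- **Data.** The comparison is made "Once data is collected for 20 patients undergoing Magtrace, and 20 patients undergoing routine care".
- **Uncertainty.** The plan reads: "Sensitivity analyses will be performed on this dataset to measure the robustness of the findings to changes in the values of the parameters measured". These are the quantities that the research staff time by stopwatch. The intervals are drawn from that step: "Rather than relying on point-estimates, this will enable the derivation of credible intervals". A second aim, given in the same sentence, is to show "how specific factors such as time in the hospital, number of visits, requirement for isotopes etc. each individually affect the overall cost".
- **Chance imbalance.** The text then says that differences between the groups, including those that arise from sampling, are accounted for in the costing in this way.
- **Bootstrapping.** It is named twice, each time for another purpose. If key covariates are imbalanced after randomisation, outcomes are adjusted "using gold-standard two-stage bootstrapping for costeffectiveness analyses". For the annual projection and return on investment, the plan is "bootstrapping from this cohort of patients to a larger group representative of the full spectrum of clinical caseload".

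Section 10.3 (Analysis) only refers back to this text. No interval level, input distribution, prior, SD or correlation is given for the cost comparison.

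**The concern.** A sensitivity analysis asks how the result responds when an input is set to another value. An interval for the arm difference in mean cost has to answer a different question: how far that difference would move if another 20 and 20 patients had been randomised. The first does not deliver the second unless the inputs are varied jointly and with the spread and dependence that they have across patients. The protocol does not say that they will be.

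At this sample size, chance differences between arms can be large. If the interval is miscalibrated, a saving produced by chance could look established, or a real one could look uncertain. Cost per episode is listed as a secondary endpoint, but it also feeds the primary endpoint, cost effectiveness, and the annual projection for the Trust.

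**Working it through.** **1. Inputs.** From the protocol: 20 patients per arm (section 4.2). Part 1 states no interval width or power, so there is no figure of the plan's own to reproduce. Assumed for illustration: *k* cost items per patient with equal variance s² and common within-patient correlation *r*; a 95% level; and, for the one-way case, an input varied over the 95% interval of its own mean difference.

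**2. Correct variance.** The cost per patient is the sum of the *k* items. The arm difference in means with *n* per arm has variance (2/n)·k·s²·[1 + (k−1)r].

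**3. Inputs drawn separately.** The variance used is (2/n)·k·s². The ratio of its standard error to the correct one is 1/√[1 + (k−1)r].

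- k = 3: 0.85 at r = 0.2; 0.71 at r = 0.5; 0.62 at r = 0.8; but 1.29 at r = −0.2 and 2.24 at r = −0.4.
- k = 2: 0.82 at r = 0.5; 1.29 at r = −0.4.

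A ratio below 1 means too narrow, above 1 too wide.

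**4. One input varied alone.** The variance used is (2/n)·s², so the ratio is 1/√{k[1 + (k−1)r]}. At r = 0 and k = 3 this is 1/√3 = 0.58, and coverage is 2Φ(1.96 × 0.58) − 1, about 74%. This shortfall needs no correlation: the range leaves out the uncertainty of the other inputs.

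**5. Simulation.** 3,000 trials of 20 v 20, two normally distributed items, nominal 95% intervals. The bootstrap is a percentile interval from 600 resamples of whole patients within arm. The one-way column uses the more influential input. Mean widths are in SD units of one item.

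| r | Coverage: separate draws | Coverage: one-way | Coverage: whole patients | Width: separate draws | Width: whole patients |
|---|---|---|---|---|---|
| −0.5 | 99.2% | 95.8% | 93.8% | 1.75 | 1.19 |
| −0.3 | 97.2% | 90.7% | 92.2% | 1.75 | 1.41 |
| 0 | 94.4% | 84.2% | 93.0% | 1.75 | 1.69 |
| 0.3 | 92.1% | 80.7% | 94.5% | 1.75 | 1.92 |
| 0.5 | 88.4% | 75.7% | 93.8% | 1.75 | 2.07 |
| 0.8 | 86.2% | 73.5% | 93.5% | 1.75 | 2.26 |

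The width from separate draws does not respond to the correlation. Resampling whole patients does, and its coverage stays between 92.2% and 94.5%.

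**6. Sign of the correlation.** The protocol does not settle it. An extra visit would usually bring extra hours and staff minutes, which points to a positive value. But section 3 (Iron Oxide Use in Breast Surgery) describes a trade-off for Technetium: the two-day protocol adds a visit, while the one-day protocol needs a two-hour gap before surgery. Visits and hours on the day of surgery could therefore be negatively related within the control arm.

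**The case against.** The strongest reply is that this reads a faulty method into silence. Much of that reply stands.

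- A reader might infer that the intervals are to be built by changing one parameter at a time. The grammar does not support this. The sentence has two aims, and the word individually belongs to the second, which is to show what drives cost.
- A reader might infer that inputs will be treated as independent. The protocol does not say so. The analyses run on patient-level data, and both named bootstraps could keep a patient's items together.
- A reader might infer that the intervals will certainly be too narrow. That needs a positive correlation, which the protocol does not give.
- A reader might count isotope use among the correlated items. Technetium defines the control arm, so isotope use has almost no variation within an arm. It is not exactly fixed, since section 3.2 allows one tracer to replace the other when supply fails.
- The one-way figures depend on the range chosen. Varying an input over observed patient values would give much wider ranges.
- Calling the intervals credible without stating a prior is loose wording, not a demonstrated error.
- A statistical analysis plan, not at hand, may define the interval.

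The reply does not remove the stated link. The protocol itself names sensitivity analysis as the source of the intervals and as the remedy for chance imbalance, and it gives its bootstraps other jobs. If no covariate imbalance is found, no patient-level resampling is assigned to the 20 v 20 comparison.

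**Conclusion.** The point holds in a limited form. The protocol names a source for its cost intervals that does not by itself estimate the sampling error of the arm difference at 20 v 20. A one-way range would omit the other inputs' uncertainty. Separate draws would be miscalibrated whenever resource items are correlated within patients: too narrow if they rise together, too wide if they trade off.

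In the two-item illustration, separate draws cover from 86% (r = 0.8) to 99% (r = −0.5), and a one-way range from 74% to 96%, against a nominal 95%. These figures rest on assumed correlations, equal variances and normal items. They show that calibration can fail in either direction and do not predict this trial. The case for change is that a better-defined method is nearly free and uses data and a technique already planned.

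**What to change.** Replace the sentence on intervals in section 4.2 (Study design, Part 1), or define the interval in the analysis plan, along these lines: the 95% interval for the arm difference in mean cost per episode, and for any cost-effectiveness measure built on it, is obtained by resampling whole patients with replacement within each randomised arm, keeping each patient's resource items and outcome together.

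Keep one-way sensitivity analyses for unit prices and for ranking cost drivers, and report them as ranges, not as intervals. Do not rely on them to account for chance imbalance between arms.

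The cost is a few lines of wording and code, with no extra data or patients. The reported interval may be wider: in the illustration at r = 0.5, 2.07 against 1.75 for separate draws. It would be narrower if items trade off.

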#### 3.3 Potential Benefits

The potential benefits of using Magtrace® will be in simplifying the patient pathway in the pre-operative period. Magtrace® will be given on the day of surgery, whereas Technetium would be given on the day of surgery or the day before. This means around the time of surgery there will be less stress for the patient, they will be ready to have their surgery at any time of the day (rather than having to wait until they have a Technetium injection). Technetium requires aliquoting out from the Christie and transporting across to the Nuclear medicine department on a daily basis, and following radioactive licences, must be given by two trained professionals in a very controlled manner. Magtrace® can be given by any trained member of staff without the need for ARSAC radioactivity licences. It will negate the need for the complex process of transferring the Nuclear medicine across the city and the need for staff to make up the injections every morning and give them to patients. Magtrace® will therefore simplify the pathway and remove multiple steps freeing up staff for other jobs. Magtrace® will make theatre scheduling in the morning easier as any patient will be available for theatre, potentially making less waiting for theatre staff and more efficient operating. It is unlikely that extra cases will be done as a result of the change but it may avoid overruns and delays in theatre.

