## 5. Selection and Withdrawal of Subjects

#### 5.1 Informed Consent

Consent for Part 1 of the study will be taken by a Consultant Breast Surgeon or Research Nurse. This consultant or research nurse will be authorised to take consent by the Chief Investigator of the study and will have received training about the study and written information about the study. This consent process will take place at Study Visit 1, for Part 1 patients, more than 24 hours after initial invitation to take part in the study. Consent for Part 2 (Focus Group & Survey) will be undertaken by the same staff members but will be taken at the time of introduction of the study to the patient or healthcare professional.

## 5.2 Inclusion Criteria - Part 1

- Participant is willing and able to give informed consent for participation in the study;
- Female, aged 18 years or above;
- Diagnosed with invasive breast cancer
- Willing to allow his or her General Practitioner and consultant, if appropriate, to be notified of participation in the study;

- Undergoing breast conservation surgery requiring Magseed® localisation and sentinel node biopsy
- All MRIs must be completed prior to Magseed® insertion

#### 5.3 Exclusion Criteria – Part 1

- Patients with a Pacemaker or implanted device in the chest wall;
- Patients who are pregnant or lactating;
- Patients who have received Magtrace® (iron oxide) injection in the previous six months;
- Patients with previous ipsilateral axillary surgery
- Patients whose breast and axillary surgery are not due to be performed synchronously.
- Patients following neoadjuvant chemotherapy
- Patients requiring an interpreter
- Patients involved in current research or have recently been involved in any research prior to recruitment

Patients who require MRI follow-up of the ipsilateral breast in the year following surgery (as Magtrace® may interfere with MRI)

All individuals will be considered for inclusion in this study regardless of age, disability, gender reassignment, marriage and civil partnership, pregnancy and maternity, race, religion and belief, sex, and sexual orientation except where the study inclusion and exclusion criteria EXPLICITLY state otherwise

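### Resampling the 40 Part 1 patients cannot represent the full annual caseload, and any interval read from an enlarged resample would be too narrow

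*Protocol*

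**What the plan says.** Section 4.2 of the protocol, Study design (Part 1), sets the data for the economic comparison: "Once data is collected for 20 patients undergoing Magtrace, and 20 patients undergoing routine care". It then treats these patients as an estimation set for a year of activity: "results observed in this cohort of 40 patients (representative sample) may then be extrapolated to all expected patients/caseload over the course of a calendar year". The means of doing so is "bootstrapping from this cohort of patients to a larger group representative of the full spectrum of clinical caseload over a calendar year". The output claimed for this step is that it "will enable determination of the expected return-on-investment of switching from Technetium nuclear medicine to Magtrace® at the Trust level". Partial uptake is allowed for as well, with a range described as "various levels of implementation/caseload, from 0 to 100" per cent. No annual caseload and no resample size are given.

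Intervals appear slightly earlier in the same section, in connection with sensitivity analyses on the observed dataset: "Rather than relying on point-estimates, this will enable the derivation of credible intervals". No interval is mentioned for the return on investment itself.

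Sections 5.2 and 5.3 define who can be among the 40. All are women with invasive cancer having breast conservation with Magseed localisation and a sentinel node biopsy. Those excluded include patients treated with neoadjuvant chemotherapy, those with earlier axillary surgery on the same side, those whose breast and axillary operations are staged, those with a chest-wall implant, those who need an interpreter, and "Patients who require MRI follow-up of the ipsilateral breast in the year following surgery (as Magtrace® may interfere with MRI").

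**The concern.** Two things are asked of the bootstrap that it cannot do.

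The first is coverage of case types. A bootstrap draws with replacement from the patients in hand. Making the draw larger gives more copies of those patients and never a kind of patient who was not enrolled. A resample of the 40 therefore stays a resample of patients who meet sections 5.2 and 5.3, however large it is made.

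The second is precision. The spread of a resampled mean depends on how many patients are drawn in each replicate. Drawing more than were observed treats copies as independent information. The projected return on investment could then appear much more certain than 20 patients per arm allow.

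At stake is the projection to Trust level, which is the step that turns the 40-patient comparison into a statement about switching the service.

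**Working it through.** **Population.** Setting the sections side by side is enough. Section 4.2 claims an enlarged group that represents the whole clinical caseload of a year. Sections 5.2 and 5.3 limit the source to one surgical pathway and remove the groups listed above. The probability that an excluded type of patient appears in a resample is zero at any resample size. Multiplying the number of draws does not change the mix of case types, so the stated method cannot deliver the stated property.

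**Precision.** Inputs: n = 20 per arm (section 4.2). M, the number drawn per arm in each replicate, is an assumption, because the protocol gives neither M nor a caseload. Let s be the standard deviation of cost per patient, taken as equal in the two arms.

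- Standard error of the difference in mean cost from 20 per arm: s × sqrt(2/20).
- Bootstrap standard error when M per arm are drawn: s × sqrt(2/M).
- Ratio of widths: sqrt(20/M). The value of s cancels.
- Actual coverage of a nominal 95% interval, by normal approximation: 2Φ(1.96 × sqrt(20/M)) − 1.

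Example at M = 100: sqrt(20/100) = 0.447; 1.96 × 0.447 = 0.877; coverage 61.9%.

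The formula was checked by simulation: lognormal costs with assumed coefficients of variation (CV) of 0.3, 0.6 and 1.0, no true difference, 2,000 trials, 500 resamples each, percentile interval for the difference in means.

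| M per arm (assumed) | Width relative to M = 20 | Coverage, formula | Coverage, simulated (CV 0.3 / 0.6 / 1.0) |
|---|---|---|---|
| 20 | 1.00 | 95.0% | 93.6% / 92.0% / 90.6% |
| 50 | 0.63 | 78.5% | not run |
| 100 | 0.45 | 61.9% | 59.0% / 58.8% / 54.8% |
| 200 | 0.32 | 46.5% | 45.8% / 44.4% / 41.0% |
| 500 | 0.20 | 30.5% | 27.9% / 30.6% / 27.8% |
| 1000 | 0.14 | 21.8% | 20.4% / 19.9% / 19.3% |

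A separate simulation with gamma costs (CV 0.5; 1,500 trials, 300 resamples) gave 74.7% at M = 50.

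In units of s, the 95% half-width that 20 per arm supports is 1.96 × sqrt(2/20) = 0.62. Read from a resample of 500 per arm it would appear as 0.62 × 0.20 = 0.12.

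**What is not affected.** The average of the resampled means equals the observed mean for every M. The estimated cost difference per patient is therefore the same whatever the resample size. Only a stated precision can go wrong.

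**Scaling.** If each replicate draws 20 per arm and its mean difference is multiplied by an annual number of patients, the estimate and its interval grow by the same factor. Relative precision stays at what 20 per arm supports, whatever the caseload.

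**The case against.** The strongest reply is that the protocol never says an interval will be taken from the enlarged resample. It promises an expected return on investment, which is a mean, and ties credible intervals to sensitivity analyses on the 40-patient data. This stands. A reader might infer that the plan will produce intervals that are far too narrow. The text does not say so, and the coverage figures apply only if an interval is read from that step. The condition is not remote, however. Enlarging the resample leaves the expected mean unchanged, so apparent precision is all that it alters, and the same section says it wants more than point estimates.

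It can also be said that simulating a year's patients is legitimate. This is so when the simulation is nested inside an outer bootstrap of the original size. Section 4.2 neither describes nor excludes such nesting. The two-stage bootstrap that it mentions is offered as adjustment for imbalance after randomisation and is not linked to the caseload step. A statistical analysis plan could settle the resample size, but the protocol already fixes the direction (a larger group) and the claim made for it.

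Two further inferences are tempting and not supported:

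- **A 100% scenario must include patients kept away from Magtrace, so a Technetium service would have to continue.** The denominator of the 0 to 100% range is not defined, and trial exclusions are not clinical bars. A reason specific to Magtrace is attached only to the MRI exclusion. Section 3.2 calls both tracers standard of care, each used when the other is unavailable.
- **Staff minutes saved are wrongly counted as money.** Section 3.3 does say "It is unlikely that extra cases will be done as a result of the change", but the same sentence goes on to mention fewer overruns and delays. Valuing time at salary cost is the declared costing method, and the protocol does not claim that cash is released. Reporting the two separately is a preference.

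**Conclusion.** The population point holds without condition. The 40 patients cannot be made to represent the full caseload by resampling, and section 4.2 must be reconciled with sections 5.2 and 5.3.

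The precision point holds conditionally. An interval read from M per arm would be too narrow by sqrt(20/M), with coverage of 78.5%, 61.9% or 30.5% at an assumed M of 50, 100 or 500. The width ratio does not depend on the cost variance. The coverage figures rest on the normal approximation, and the simulations with skewed costs came out close to it or somewhat lower.

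The randomised comparison and the cost difference per patient are untouched, and return on investment is not among the listed endpoints. A reader might conclude that the projected saving per patient is overstated; nothing in the resample size supports that. This is a point that should be fixed, and it does not threaten the primary endpoint.

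**What to change.** In section 4.2:

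1. State that every bootstrap replicate draws 20 patients per arm with replacement (or the number actually observed per arm). If a year's patients are to be simulated, nest that simulation inside such a bootstrap.
2. Multiply each replicate's mean cost difference by the annual number of patients who meet sections 5.2 and 5.3, and take the interval from those products. State that number and its source.
3. Replace the reference to the full caseload with that eligible population, and use it as the denominator of the 0 to 100% range.
4. Show any wider caseload only as a labelled scenario, with its assumptions about the unobserved groups written out.

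This changes analysis wording only and needs no further patients or data collection from participants. The price is intervals wider than an enlarged resample would show, and a projection that covers fewer patients. Even at 20 per arm, the percentile interval covered only 90.6% to 93.6% with skewed costs in the simulations above, so its limits should be read with some caution.
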